TNBC patients are known to be rapidly progressive and have a poor prognosis. This poor prognosis is due to the lack of common breast cancer targets in TNBC. As TNBC expresses CAIX, we plan to evaluate CAIX targeting by using a radiolabeled monoclonal antibody that recognizes carbonic anhydrase IX (CAIX) (^{89}Zr -girentuximab otherwise known as ^{89}Zr -TLX250). Previous and ongoing studies have demonstrated the potential application of ^{89}Zr -TLX250 as a new PET/CT imaging tracer for the detection of renal cancer.

After establishing the TNBC targeting properties of the ^{89}Zr -TLX250 PET/CT imaging tracer, it should be interesting to develop a new targeted therapy using TLX250- radiolabeled with a therapeutic radionuclide such as $^{177}\text{Lutétium}$.

ABBREVIATIONS AND DEFINITION OF TERMS

The following abbreviations and special terms are used in this study Clinical Study Protocol.

Abbreviation or special term	Explanation
¹⁸ F	Fluor-18
¹²⁴ I	Iodine-124
¹¹¹ In	Indium-111
¹⁷⁷ Lu	Lutetium-177
⁸⁹ Zr	Zirconium-89
ADL	Activities of Daily Living
AE	Adverse event
ALAT	Alanine aminotransferase
ANSM	French Health Authority
ASAT	Aspartate aminotransferase
ATZ	Acetazolamide
B-HCG	Beta human chorionic gonadotropin
BP	Blood Pressure
CA IX	Carbonic anhydrase IX
CA 15-3	Cancer antigen 15-3
CEA	carcinoembryonic antigen
CPP	French Ethics Committee
CT	Computed tomography
DSUR	Development Safety Update Reports
eCRF	Electronic case report form
EMA	European Medicines Agency
ER	Estrogen Receptor
EOS	End Of Study
EVCTM	EudraVigilance Clinical Trial Module
FDG	Fluorodésoxyglucose
FU	Follow up
GCP	Good Clinical Practice
GMP	Good Manufacturing Practice
GLP	Good Laboratory Practice
HACA	Human Anti-Chimeric Antibodies
HER 2	human Epidermal growth factor Receptor 2
HIF1 α	Hypoxia-Inducible Factor 1-alpha
HSA	Human Serum Albumin
ICF	Informed consent form
ICH	International Conference on Harmonization
IEC	Independent Ethics Committee
IHC	ImmunoHistoChemistry
IV	Intravenous(ly)
mAb	Monoclonal antibody
MedDRA	Medical Dictionary for Regulatory Activities
MBq	Mega Becquerel
NCI CTCAE	National Cancer Institute Common Terminology Criteria for Adverse Events

Abbreviation or special term	Explanation
PD-L1	Programmed death-ligand 1
PET	Positron-emission tomography
PK	Pharmacokinetic(s)
PR	Progesterone Receptor
PTX	Paclitaxel
SAE	Serious adverse event
SID	Subject identification
SUSAR	Suspected unexpected serious adverse reaction
SUV	Standardized uptake value
TEAE	Treatment-emergent adverse event
TNBC	Triple Negative Breast Cancer
UAE	Unexpected Adverse Event
WB	Whole Body
WHO	World Health Organization

HISTORY OF PROTOCOLE AMENDMENTS

	Version number / Date (after amendment)	Justifications of amendment
Initial authorisation	V1.2 du 29/03/2021	Initial authorized version
Substantial Amendment 1	V2 du 21/06/2022	18-month extension of the recruitment period Inclusion criteria 4 modified

Short Title : **OPALESCENCE**
Ref ICO : ICO-2020-25
N° EudraCT : 2020-003805-71

TRIAL CALENDAR

NUMBER OF EXPECTED PATIENTS	12 patients
DURATION OF ENROLMENT PERIOD :	30 months
DURATION OF PROCEDURE / DURATION OF FOLLOW-UP :	5 days / 3 months
MAXIMUM TIME OF PARTICIPATION PER PATIENT :	4 months (including approximately 1 month for the inclusion assessment)
GLOBAL DURATION OF THE TRIAL :	33 months
END OF THE CLINICAL TRIAL :	Last visit of the last enrolled patient

CONSIDERED DURATION UNTIL THE ANALYSIS OF THE PRIMARY OBJECTIVE :	45 months (33 + 12 months data analysis)
INTERIM ANALYSIS :	NA

SCHEDULE OF STUDY ASSESSMENTS

Visit	Screening	89Zr- Girentuximab PET/CT					FU # 1	End of Study
Day	-30 to -1	0	1	3	5^(f)	7	30	90
Written informed consent	X							
Formal verification of eligibility criteria	X							
Medical and disease history	X							
Enrolment	X							
Physical Exam								
Physical examination, Weight	X							
WHO performance status	X						X	
Vital signs (temperature, respiratory rate, blood pressure, pulse)	X							
Laboratory Exam								
Haematology and Serum chemistry ^(a)	X				X			
Tumor Biomarkers: CEA, CA 15-3	X							
Pregnancy test ^(e)	X							
Imaging								
FDG PET/CT scan with contrast agent injection	X							X ^(g)
CT scan								X ^(g)
89Zr-Girentuximab PET/CT Imaging								
89Zr-Girentuximab administration		X						
Whole body PET imaging					X			
Ancillary study : 89Zr-Girentuximab biodistribution								
89Zr-Girentuximab imaging Biodistribution ^(c)		X	X	X	X	X		
89Zr-Girentuximab Blood pharmacokinetics ^(d)		X	X	X	X	X		
Histological Analysis								
New or archival Tumor Histology	X							
Safety								
Baseline findings / AE / SAE assessments	X	X	X	X	X	X	X	X
Concomitant medications	X	X	X	X	X	X	X	X
Antidrug Antibody HACA blood sample	X							X
Vital signs ^(b)		X						

- (a)** Blood count, creatinine clearance, glucose, bilirubin, ALAT, ASAT, Alkaline Phosphatases, Gamma GT.

1. INTRODUCTION

1.1 Disease background

Triple-negative breast cancer (TNBC) is associated with a high risk of recurrence and generally a bad prognosis. More than one-third of patients with TNBC will present distant metastases during the course of their disease. Although chemotherapy has been the main treatment option for metastatic TNBC for a long time, this scenario has changed recently with the results of immunotherapy in patients with PD-L1-positive tumors. In patients with PD-L1-positive or negative tumors, a single agent chemotherapy metastatic first-line treatment regimen containing taxanes with or without bevacizumab could be used.

The treatment of TNBC is constantly evolving. To improve metastatic TNBC treatment outcomes, patients are encouraged to enroll in ongoing trials which are evaluating new targeted agents, immunotherapy and predictive biomarkers (1,2).

Since Warburg introduced the so-called Warburg effect, characterized by unregulated glucose uptake and disruption of glycolytic metabolism in cancer cells, dysregulated energy metabolism has become known as an important part of the pathogenesis of uncontrolled growth in cancer cells (3). TNBC have generally been shown to have an exacerbated glycolytic metabolism when compared to non-TNBC (4,5).

Recent insight on regulation of glycolysis suggests hypoxia-inducible factor 1-alpha (HIF1 α) as a key regulator that enables tumor cells to survive by altering glucose metabolism (6). HIF1 α is controlled by oxygen levels and is stabilized under hypoxic conditions. Stabilized HIF1 α activates transcription of several genes implicated in glycolytic cancer metabolism, by increasing glucose transporter expression. This accelerates influx of glucose into tumor cells, and subsequent glycolysis results in tumor microenvironment acidosis (7). In order to overcome acidity, these microenvironmental stresses activate transcription of compensatory genes including the gene encoding carbonic anhydrase IX (CAIX), a member of metalloenzyme family that is a major downstream target of HIF1 α (3,8,9).

Based on these well characterized metabolic pathways in cancer cells and the tumor microenvironment, we propose to focus on the targeting of CAIX in TNBC.

1.2 Procedure background/non-clinical and clinical experience

CAIX is normally expressed in intestinal and stomach mucosa, gallbladder and testis (10), but is upregulated in several forms of cancer, including breast cancer. Indeed, CAIX is a marker for hypoxic

regions of breast tumors (9,11) and is associated with poor prognosis (12–14) and high-grade, ER-negative breast tumors (15). Its role in tumor growth and disease progression has been attributed to its ability to reduce pericellular pH in response to hypoxia (15–17), creating a toxic environment for normal cells (18). Acidic environments also facilitate the breakdown of the tumoral extracellular matrix (19) which can enhance metastatic activity (20,21).

Several studies have identified altered HIF1 α and CAIX protein expression levels to be related to poor prognosis in breast cancer (14,22–26). CAIX is expressed in 7 % of an unselected breast cancer cohort and in 25 % of TNBCs (27). CAIX expression rates increased with tumor grade ($p < 0.001$) and associations with tumor size were significant for CAIX ($p < 0.001$; positive association). Although based on only a few studies, CAIX showed profound lower expression rates in normal breast tissue and benign breast disease ($p < 0.001$), and high rates in carcinoma in situ (28). The expression levels of HIF1 α and CAIX vary depending on the intrinsic subtype, and they are increased in TNBC compared to other subtypes (22).

Three studies have investigated HIF1 α and glucose metabolism for alternative therapeutic options to overcome breast cancer resistance to adjuvant therapeutic modalities (24,29,30). More recently, in early TNBC, combined HIF1 α and CAIX protein expression may serve as an unfavorable prognostic indicator, particularly in patients receiving a cyclophosphamide-based chemotherapy or radiotherapy as well as those with basal phenotype of breast cancer (31).

CAIX has recently emerged as a very attractive therapeutic target due to the following features:

1. CAIX shows a tissue-restricted pattern and low expression levels in normal tissues, while it is induced in a broad range of cancers (32);
2. It is located on the surface of cells (33);
3. Its overexpression in cancers confers a survival advantage in hypoxia and facilitates cell migration and metastasis (34).

Depletion of CAIX in cancer cell lines has been shown to attenuate the growth of tumor xenografts and inhibit the formation of spontaneous metastasis (35). Interestingly, CAIX was found to contribute to cell migration and invasion by facilitating formation of focal adhesions, ion-transport and pH control at the leading edge of lamellipodia of moving cells (36). Currently, substantial effort is devoted to the development of potent, cancer-selective CAIX inhibitors, including monoclonal antibodies (37). Moreover, recently, Chafe et al., suggested that targeting CAIX in the tumor microenvironment in combination with immune-checkpoint blockade is a potential therapeutic strategy for enhancing response and survival in patients with hypoxic solid malignancies (38). Another team developed a CAIX-targeted, human serum albumin (HSA) drug delivery vehicle which contained the potent anticancer drug, Paclitaxel (PTX). They used Acetazolamide (ATZ), a small molecule ligand of CAIX to selectively deliver HSA-PTX to TNBC cells (39).

1.3 Rationale for conducting this study

Metastatic TNBC, due to its lack of usual BC target expression, its poor prognosis and the expression of CAIX in 25% of cases, seems to be an interesting clinical indication for studying CAIX targeting

using a radiolabeled monoclonal antibody that recognizes carbonic anhydrase IX (⁸⁹Zr-Girentuximab or otherwise known as ⁸⁹Zr-TLX250).

⁸⁹Zr-Girentuximab is under clinical development as a PET/CT imaging tracer for the detection of renal tumor masses and metastases (which overexpress CAIX). When the anti-CAIX antibody, girentuximab is labelled with a PET radionuclide such as ⁸⁹Zirconium, it can be used as an imaging probe for PET. After intravenous administration of this imaging agent, the tumor, lymph nodes and distant metastases can be non-invasively assessed using whole-body PET imaging. There is extensive clinical evidence demonstrating the ability of girentuximab-radiolabeled with PET radionuclides (Immuno-PET) to target CAIX lesions in patients with different type of solid tumors (37,40-42)

While there is a lack of expression of common BC targets in TNBC, it is well known that 25% of TNBCs express CAIX, therefore there is a strong rationale for using a radiolabeled CAIX-targeting monoclonal antibody to detect and image TNBCs. At present, FDG PET is routinely used to image breast cancer and we propose to compare the detection sensitivity of ⁸⁹Zr-Girentuximab with FDG PET. In addition, we would like to assess the biodistribution and dosimetry of the radiopharmaceutical in metastatic TNBC patients with the objective of defining any possible future theranostic applications.

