4.2 Inclusion criteria

Patients must meet all of the following inclusion criteria to be eligible for enrolment into the study:

1. Written informed consent obtained from the patient prior to performing any protocol-related procedures, including screening evaluations.
2. Female or male, Age \geq 18 years at time of study entry.
3. Primitive triple negative breast cancer proven histologically, defined according to the following criteria:
 - ⇒ Estrogen receptors \leq 10%.
 - ⇒ And progesterone receptors \leq 10%.
 - ⇒ And HER2 not amplified or not overexpressed.
4. Metastatic Breast Cancer documented by conventional imaging and/or FDG PET/CT with at least one measurable metastatic lesion according to RECIST and/or PERCIST.
5. Consent to use a contraception method for at least 30 days after administration of ^{89}Zr -TLX250.
6. ECOG Performance Status 0 or 1.
7. Life expectancy at least 6 months.
8. Patient has valid health insurance.
9. Patient is willing and able to comply with the protocol for the duration of the study including undergoing treatment and scheduled visits and examinations including follow up.

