6.7 Independent Central Histological analysis

An independent central histology analysis will be carried out at ICO Saint Herblain. The purpose of this analysis is the determination of the degree of CAIX expression from the biopsy tumor sample.

The degree of CAIX expression will be investigated and classified.

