8.2 Determination of sample size

As this study is a proof-of-concept, exploratory and descriptive pilot study, the sample size determination is not based on statistical considerations, it is planned to enrol 12 evaluable patients.

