8.8 Description of analysis sets

8.8.1 For Safety Analysis Set:

The frequency and severity of the clinical and biological effects collected over a period of 15 days then at 3 months following the completion of the ^{89}Zr -TLX250 PET/CT will be described by means of frequency of their respective modalities. HACA test at the visit at 3 months post ^{89}Zr -TLX250 PET/CT.

8.8.2 For the determination of ^{89}Zr -TLX250 PET-CT preliminary analysis of diagnostic performance:

From the reference ("gold standard") determined for each patient from all imaging and histology screening data and/or 3-months imaging follow-up (RECIST 1.1 criteria, or PERSIST criteria). The reporting qualitative and semi-quantitative parameters of the lesions will be established at D5 post-injection. The diagnostic performance of ^{89}Zr -TLX250 PET/CT obtained at the post-injection delay considered optimal related, ^{18}FDG PET/CT scan and CT scan compared to gold standard will be described by the sensitivity, specificity, positive and negative predictive values (with their 95% CI) and compared by means of Mc Nemar test. Concordance between techniques will be described by means of Kappa.

Total number of lesions (gold-standard) will be the number of lesions identified by at least one modality.

Lesion detection rates per imaging modality and combined imaging modalities (CT combined with PET) will be estimated with their 95% CI and compared by Wald test, overall and according to organ sites.

Agreement in detecting lesions between modalities will be assessed using kappa's (95%CI).

Furthermore, we will compare the median number of affected organ sites across patients assessed by ^{18}FDG -PET/CT or ^{89}Zr -girentuximab-PET/CT using Wilcoxon signed rank tests.

The physiological biodistribution of ^{89}Zr -girentuximab will be described in normal tissues (lung, liver) using geometric mean SUVmean.

Short Title : **OPALESCENCE**
Ref ICO : ICO-2020-25
N° EudraCT : 2020-003805-71

The overall geometric mean ⁸⁹Zr-girentuximab or ¹⁸FDG SUVmax will be used to quantify uptake in lesions. Link between uptake and lesions location and lesions diameter on CT will be tested.

Correlation between ¹⁸FDG -uptake and ⁸⁹Zr-girentuximab-uptake will be calculated by Rho's coefficient (Spearman test).

8.8.3 For ancillary study set:

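### CAIX is expected in about a quarter of TNBC and patients are not selected on it, so a low 89Zr-to-FDG ratio cannot be attributed to absent target or tracer failure; the planned CAIX endpoint omits the tracer-negative lesions that would help.

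*Combined protocol and SAP*

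**What the plan says.** - **Expected target expression.** Section 1.2 states that "CAIX is expressed in 7 % of an unselected breast cancer cohort and in 25 % of TNBCs". Section 1.3 names "the expression of CAIX in 25% of cases" among its reasons for the study and repeats that "it is well known that 25% of TNBCs express CAIX". Neither section gives the staining cut-off behind the figure.
- **Eligibility.** Section 4.2 requires "Primitive triple negative breast cancer proven histologically", defined by ER, PR and HER2. Sections 4.2 and 4.3 contain no CAIX criterion.
- **Primary endpoint (2.1.2, repeated in 8.1.2).** Per-lesion concordance of 89Zr-TLX250 with FDG and CT, expressed as lesion-count ratios.
- **Analysis (8.8.2).** Sensitivity, specificity, predictive values, McNemar, kappa and detection rates. The detection rates are given "overall and according to organ sites". CAIX is not mentioned.
- **CAIX histology.** Section 6.7 plans central "determination of the degree of CAIX expression from the biopsy tumor sample". The objective (2.2.1 item 2) applies only if there is a biopsy. The endpoint (2.2.2 item 2, repeated as item 5 in 8.1.4) covers 89Zr-positive lesions among biopsied metastases. Section 5.2.3.2 compares SUV with CAIX on a 5-point scale, without the 89Zr-positive limit and without a positivity cut-off.
- **Tissue.** The schedule of assessments marks "New or archival Tumor Histology" at screening.
- **Sample size (8.2).** "the sample size determination is not based on statistical considerations, it is planned to enrol 12 evaluable patients".

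**The concern.** The tracer binds CAIX, whereas FDG shows glucose metabolism. If most tumours lack CAIX, a tracer that works exactly as intended will disagree with FDG in most lesions. The primary ratio is thus a product of two unknowns: how often the target is present, and how often the tracer shows it when it is.

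The plan also reads this one number in two ways. The ratio of 89Zr-positive to FDG-positive lesions is part of the primary concordance, and secondary endpoint 1 (2.2.2) presents it as the CAIX-positive share of tumour burden. The second reading takes for granted that uptake equals expression.

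Sections 1.4.2 and 1.4.4 look ahead to a companion diagnostic and a 177Lu therapy. For that purpose it matters whether a low ratio points towards selecting patients on CAIX or towards doubt about the agent. The data that bear on this are lesions with known CAIX status that the tracer did not show, and the CAIX endpoint as worded excludes them.

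**Working it through.** **Plan's own figure.** The sample size of 12 has no stated statistical basis, and no target concordance or precision is given. There is nothing to reproduce.

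**Inputs.** n = 12 (8.2); CAIX prevalence 25% (1.2, 1.3). All other values below are assumptions and are labelled as such.

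**1. The ratio as a mixture.** Let p be the share of FDG-positive lesions that express CAIX, s the share of those that the tracer shows, and f the share of CAIX-negative lesions that it shows. Then

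ratio = p × s + (1 − p) × f.

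With f = 0 and lesion counts unrelated to CAIX status (both assumed):

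| p | s | ratio |
|---|---|---|
| 0.25 | 1.00 | 0.25 |
| 0.40 | 0.625 | 0.25 |
| 0.50 | 0.50 | 0.25 |
| 1.00 | 0.25 | 0.25 |

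The ratio alone cannot distinguish these rows.

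**2. Kappa for a perfect tracer.** Section 5.2.3.1 calls a lesion tracer-positive only at an FDG-positive site. Let q be the share of all lesions that FDG finds (assumed) and r = 0.25 the ratio above. Observed agreement is qr + (1 − q); chance agreement is q × qr + (1 − q)(1 − qr).

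At q = 0.80, observed = 0.20 + 0.20 = 0.40, chance = 0.16 + 0.16 = 0.32, and kappa = 0.08 / 0.68 = 0.12. At q = 0.90, 0.95 and 1.00, kappa is 0.06, 0.03 and 0.00. A fully working tracer would look like almost no agreement.

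**3. How many CAIX-positive patients.** If CAIX is all-or-none within a patient (assumed), the count is Binomial(12, 0.25): expected 12 × 0.25 = 3, central 95% range 0 to 6. P(0) = 0.75^12 = 3.2%; P(2 or fewer) = 39%. With equal lesion counts per patient, a perfect tracer's ratio would range from 0/12 = 0 to 6/12 = 50% by chance.

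Other prevalences (assumed):

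| Prevalence | Expected of 12 | P(none) |
|---|---|---|
| 15% | 1.8 | 14.2% |
| 25% | 3.0 | 3.2% |
| 35% | 4.2 | 0.6% |
| 50% | 6.0 | 0.02% |

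**4. What a CAIX split can deliver.** If a share b of patients has graded tissue (assumed), the expected number of CAIX-positive patients with tissue is 12 × 0.25 × b, and P(none) = (1 − 0.25b)^12.

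| b | Expected | P(none) |
|---|---|---|
| 25% | 0.75 | 46% |
| 50% | 1.5 | 20% |
| 75% | 2.25 | 8% |
| 100% | 3 | 3% |

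Even if all of 3 CAIX-positive patients were tracer-positive, the exact lower 95% limit is 0.025^(1/3) = 29%, so the interval is 29% to 100%.

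**5. What the planned CAIX endpoint covers.** An FDG-positive, 89Zr-negative metastasis graded CAIX-positive would point to tracer failure; one graded CAIX-negative would point to absent target. Section 2.2.2 item 2 excludes both. Section 5.2.3.2 would admit them, so the two sections differ in scope.

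**The case against.** The study is declared exploratory and descriptive, has no statistical termination rule (8.6) and tests no target concordance. For a possible companion diagnostic, the detection rate in unselected patients is informative in itself. The plan also has an SUV-versus-CAIX comparison, which 9.2.2 lists among its major secondary endpoints. All of this stands. It is why the unselected result should remain primary, and why this is a problem of interpretation and not an error in the sample size.

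It does not remove the point. The SUV-versus-CAIX endpoint omits tracer-negative lesions, and 8.8.2 contains no CAIX analysis.

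Four stronger readings are tempting, and the documents do not support them:

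- *CAIX status will be available for every patient, so one more table settles the matter.* The objective is conditional on a biopsy, 6.7 speaks of the biopsy sample, and the schedule row on histology does not mention CAIX. Section 6.1 asks for histopathology reports to be recorded, so that row may mean no more than report review. Nothing shows that archival tissue goes to central CAIX grading.
- *Tracer performance can be concluded from the CAIX-positive stratum.* With about 3 patients it cannot.
- *About three quarters of patients will be discordant.* The 25% is a tumour-level figure without a cut-off. Section 1.2 says expression rises with grade and is positively associated with tumour size, so carrying the figure over to metastases is an assumption.
- *A low ratio would trigger opposite programme decisions.* The plan contains no such decision rule.

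It is also fair to say that one biopsy, or archival tissue, does not give the CAIX status of every metastasis. Some ambiguity will remain after the fix.

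**Conclusion.** The point holds as one of interpretation. With 25% expected expression, no selection on CAIX and no analysis by CAIX, a low 89Zr-to-FDG ratio cannot be attributed to absent target or to tracer failure. A perfect tracer at 25% prevalence and one with 50% sensitivity at 50% prevalence both give 0.25. This rests on no uptake in CAIX-negative lesions and on lesion counts unrelated to CAIX status. Changing those assumptions changes the number, but the ratio remains a mixture.

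CAIX histology is foreseen but biopsy-dependent, has no positivity cut-off, is restricted in its endpoint to tracer-positive lesions, and is not connected to the primary analysis. No figure in the plan is wrong. The change should be made because it improves what the trial can say at little cost; it will reduce the ambiguity without resolving it.

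**What to change.** 1. In 2.2.2 item 2 and its repeat in 8.1.4, remove the restriction to 89Zr-positive lesions, so that every biopsied metastasis with a CAIX grade enters the SUV-versus-CAIX comparison. This also brings the endpoint into line with 5.2.3.2.
2. In 8.8.2, tabulate concordance and 89Zr detection descriptively by central CAIX result: positive, negative, not available. Fix the positivity cut-off on the 5-point scale before the images are read. Show lesion-level status (the biopsied metastasis itself) apart from patient-level status (any other tissue).
3. Keep the unselected result as primary. State that the CAIX table serves to interpret a low ratio and is not the basis for a conclusion on tracer performance.

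**Cost.** A few lines of text, a cut-off agreed in advance and one descriptive table, limited to tissue graded under 6.7. No extra patients, readers or procedures. SUV is needed at the site of tracer-negative biopsied lesions, which 5.2.3.2 already foresees by asking for it in each tumour lesion.

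**Downside.** The CAIX-positive row will be very small and may be empty, the not-available row may be large, and archival tissue may not reflect the metastases.
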